11.9. Analysis of immunogenicity

The analysis will be performed on the immunogenicity ATP (per-protocol) cohort. If the percentage of vaccinated subjects with serological results excluded from the ATP cohort for analysis of immunogenicity is more than 10%, a second analysis will be performed on the TVC.

11.9.1. Within groups assessment

Humoral immune response

For each group and at each timepoint during which blood samples are collected for humoral immune response (at Day 1, Day 31, Day 61, Day 91, Day 271 and at Day 451), and for each component (PD, PE, PilA and UspA2), the following will be computed:

- Seropositivity rate (i.e, percentage of seropositive subject) and the associated exact 95% CI
- GMCs and the associated 95% CI

The distribution of antibody concentrations will be investigated using Reverse Cumulative Curves.

A seropositive subject is a subject whose antibody concentration is greater than or equal to the assay cut-off value, as specified in [Table 10](#).

11.9.2. Between groups assessment

Comparative analyses will be exploratory with the aim to characterise the difference between the 2 groups in humoral immune response.

The difference in terms of GMCs will be evaluated at 1 month post-Dose 2 by computing the 95% CIs of the GMC ratio between groups by using an ANCOVA model on the logarithm base10 transformation of the concentrations. This model will include the group (vaccine or control), age category (40 - 59 years or 60 - 80 years), GOLD grade (GOLD 2, GOLD 3 or GOLD 4) and country as fixed effects and pre-Dose 1 concentration (as covariate).

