6.2.2.2. Treatment allocation to the subject

The treatment numbers will be allocated by dose.

6.2.2.2.1. *Study group and treatment number allocation*

The target will be to enrol approximately 600 eligible subjects who will be randomly assigned to two study groups in a (1:1) ratio (approximately 300 subjects in each group).

Allocation of the subject to a study group at the investigator site will be performed using a randomisation system on internet (SBIR). The randomisation algorithm will use a minimisation procedure accounting for age (40 - 59 years or 60 - 80 years), number of moderate/ severe AECOPD in the previous year (< 2 or ≥ 2), GOLD grade (GOLD 2, GOLD 3 or GOLD 4) and country. Minimisation factors will have equal weight in the minimisation algorithm.

Details on the minimisation algorithm are reported in the statistical analysis plan.

At Visit 1, before administration of vaccine Dose 1 to eligible subjects who signed and dated the ICF at the Screening Visit, the study staff in charge of the vaccine administration will access SBIR. Upon providing the subject's age category (40 - 59 years or 60 - 80 years), number of moderate/ severe AECOPD in the previous year, his/ her GOLD grade and subject identification number, the randomisation system will determine the study group and will provide the treatment number to be used for the first dose.

The number of each administered treatment must be recorded in the eCRF on the Vaccine Administration screen.

When SBIR is not available, please refer to the SBIR user guide or the Study Procedures Manual (SPM) for specific instructions.

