11.8. Analysis of efficacy

The primary analysis will be performed on the mTVC and repeated on the TVC **and the FAS**. The primary analysis will also be repeated on the efficacy ATP (per-protocol) cohort if the percentage of vaccinated subjects excluded from the ATP cohort for efficacy is more than 5%.

Efficacy – Clinical Endpoint

The following incidence rates of AECOPD (any type) occurring from enrolment up to 1 month post-Dose 2 will be computed together with **95% CI**, and incidence rates together with VE in the prevention of AECOPD (any type) will be computed over a period starting 1 month post-Dose 2 and lasting for 1 year, with **95% CI**:

- All-cause moderate and severe AECOPD (primary endpoint).
- All-cause, all-severity AECOPD.
- All-cause AECOPD, by severity.

For the primary endpoint, the 87% CI will also be reported in order to evaluate the null hypothesis at 13% alpha level (2-side). This objective will be considered a success if the lower limit of the 87% CI will be above 0%. (Amended 27 March 2019)

The CIs of the incidence rate will be computed using a model which accounts for repeated events. The primary outcome will be analysed using the Negative Binomial regression model with number of AECOPD as dependent variable; treatment (vaccine or placebo), age group (40–59 years or 60–80 years), GOLD grade (2, 3 or 4), history of exacerbations (<2 or ≥ 2) and country as independent variables, with logarithm as link function, and the logarithm of time for follow-up (in years) as an offset variable. If the model does not converge, the Poisson distribution will be used instead of the Negative Binomial one.

VE for AECOPD events is defined as:

$$VE(\text{AECOPD}) = 1 - R_{\text{vacc}} / R_{\text{con}}$$

with:

- R_{vacc} = average yearly incidence rate of AECOPD events per subject in the group 10-10-3-AS.
- R_{con} = average yearly incidence rate of AECOPD events per subject in the Control group.

Incidence rates of AECOPD (any type) and VE, together with 95% CI, will be computed for the following time periods:

- At Month 3, 6, 9, 12, 15 from Day 1 (cumulative)
- By 6 Months follow up period (from 1 month post-Dose 2)
- By 3 Months follow up period (from 1 month post-Dose 2)

The model used will be the same as for the primary analysis.

A sensitivity analysis **using** a permutation test will be performed for the primary efficacy endpoint.

Efficacy – Bacteriological Endpoint (PCR)

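### The exploratory GMC-ratio ANCOVA adjusts for three of the four minimisation factors and leaves out exacerbation history; adding it is a minor, nearly free improvement

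*Protocol*

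**What the plan says.** **Allocation.** Section 6.2.2.2.1 sets up a minimisation on age category, exacerbation history, GOLD grade and country. History enters as "number of moderate/ severe AECOPD in the previous year (< 2 or ≥ 2"). On weighting it says: "Minimisation factors will have equal weight in the minimisation algorithm". The synopsis and section 3 list the same four factors.

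**Primary model.** The negative binomial regression in section 11.8 has treatment, age group and GOLD grade, together with "history of exacerbations (<2 or ≥ 2) and country as independent variables". All four minimisation factors are therefore present.

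**Immunogenicity model.** Section 11.9.2 evaluates the group difference one month after Dose 2 by "computing the 95% CIs of the GMC ratio between groups by using an ANCOVA model" on log10 concentrations. It opens the list of terms with "This model will include the group (vaccine or control), age category (40 - 59 years or 60 - 80 years), GOLD grade" and completes it with "GOLD grade (GOLD 2, GOLD 3 or GOLD 4) and country as fixed effects and pre-Dose 1 concentration (as covariate"). Exacerbation history does not appear, and no reason for leaving it out is given.

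**Status.** The same section states: "Comparative analyses will be exploratory with the aim to characterise the difference between the 2 groups in humoral immune response". Section 11.11 treats secondary and tertiary comparisons as descriptive.

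**The concern.** When allocation is steered to balance a factor, that factor contributes almost nothing to the chance difference between groups. A model that omits the factor still counts its between-subject variation as residual error. The estimated standard error is then larger than the true sampling variation of the group difference, to the extent that the factor predicts the outcome. The usual remedy is to analyse by the factors used to allocate.

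The plan does this fully for the primary endpoint and for three of the four factors in the ANCOVA. The covariate list is written out, so this is not detail left to the SAP. Section 11.12 requires changes from the protocol's statistical plan to be described and justified in the final report, so the protocol is the natural place to settle it. What is at stake is the width of one exploratory confidence interval.

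**Working it through.** **1. Factors side by side**

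| Minimisation factor (6.2.2.2.1) | Primary model (11.8) | GMC-ratio ANCOVA (11.9.2) |
|---|---|---|
| Age category | yes | yes |
| Exacerbation history (<2, ≥2) | yes | **no** |
| GOLD grade | yes | yes |
| Country | yes | yes |

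The ANCOVA also has pre-Dose 1 concentration. The protocol states no standard deviation, power or sample size for the GMC ratio, so there is no figure of its own to reproduce here.

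**2. Width of the interval, by formula**

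Let R² be the share of the ANCOVA's residual variance that history explains, given the covariates already in the model. With the groups balanced on history,

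width with history omitted ÷ width with history included ≈ 1/√(1 − R²).

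The protocol gives no value for R². The range below is an assumption.

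| Assumed R² | Excess width of the CI for the log GMC ratio |
|---|---|
| 0 | 0 |
| 0.5% | 1/√0.995 − 1 = 0.25% |
| 1% | 1/√0.99 − 1 = 0.5% |
| 2% | 1/√0.98 − 1 = 1.0% |
| 3% | 1/√0.97 − 1 = 1.5% |
| 5% | 1/√0.95 − 1 = 2.6% |

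**3. Check by simulation**

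- From the protocol: four equally weighted factors, 1:1 allocation, and 600 subjects less 15% dropout, so 600 × 0.85 = 510.
- Assumed, because the protocol does not give them: biased-coin probability 0.8; eight countries; 75% of subjects in the older age category; GOLD 2/3/4 at 45/42/13%; half the subjects with two or more prior exacerbations; and the effect β of history on log concentration, in residual-SD units.
- 1,500 trials per setting, each fitted with and without history.
- Theoretical width ratio: √(1 + β²·p(1 − p)) with p = 0.5. This is the formula in step 2 with R² = β²p(1 − p)/(1 + β²p(1 − p)).

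| β (SD) | Width ratio, simulated | Width ratio, theory | Coverage, history omitted | Coverage, history included |
|---|---|---|---|---|
| 0 | 1.000 | 1.000 | 94.9% | 94.9% |
| 0.1 | 1.001 | 1.001 | 95.9% | 95.9% |
| 0.2 | 1.005 | 1.005 | 95.5% | 95.5% |
| 0.5 | 1.031 | 1.031 | 95.8% | 95.0% |
| 1.0 | 1.118 | 1.118 | 96.6% | 94.7% |

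The Monte Carlo standard error of a coverage figure is about √(0.95 × 0.05/1500) = 0.6 percentage points.

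**4. Reading the results**

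- *Bias:* the mean error of the group effect lay between −0.003 and +0.002 SD in every setting, and was practically the same in both models.
- *Mechanism:* at β = 0.5 the estimate's actual spread was 0.0889 with history omitted and 0.0890 with it included, while the mean interval width was 0.3587 against 0.3480. The estimate itself is no less precise; its standard error is overstated.
- *Direction:* the error is conservative throughout.

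**The case against.** The strongest reply is that this makes no practical difference.

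- **It is conditional.** The interval is too wide only if history predicts post-dose antibody level once pre-Dose 1 concentration, age, GOLD grade and country are in the model. Nothing in the protocol says that it does. This stands, and zero belongs in the range.
- **No decision depends on it.** The comparison is exploratory, and the only success rule in the protocol is the 87% CI for the primary endpoint. This stands too, and it is why the point is minor.
- **Models for different outcomes need not share covariates.** Exacerbation history is a natural predictor of exacerbation counts, and less obviously of antibody level. That is fair, and section 11.8 does not say that its covariates are there because of the minimisation. But the ANCOVA keeps the other three allocation factors and drops only this one without comment.
- **The analysis set is not the allocated set.** Section 11.9 runs the ANCOVA on the per-protocol immunogenicity cohort, so exclusions may loosen the balance that minimisation forced. The simulation did not model such exclusions, so its figures describe the balanced case.

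A reader might also infer that the ANCOVA's intervals do not reflect the allocation at all. The documents do not support that: three of the four factors are in the model, and one binary factor is missing.

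**Conclusion.** The omission is real, and the plan would be slightly better without it. The GMC ratio is not biased by it. The 95% CI is unaffected if history has no effect beyond the other covariates, and about 0.25% to 2.6% too wide on the log scale for an assumed partial R² of 0.5% to 5%. Reaching 3% takes an assumed effect of 0.5 SD, and 12% takes a full SD; nothing in the protocol points to effects of that size.

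It would be wrong to conclude that the type I error is inflated, that the standard error is overstated whatever the role of history, or that the primary analysis is touched. The error runs in the conservative direction, it depends on history being predictive, and the primary model already carries all four factors. These conclusions rest on the assumed R² range and on groups that remain close to balanced on history in the analysed cohort. This is a minor, nearly free improvement.

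**What to change.** In section 11.9.2, add exacerbation history to the ANCOVA as a fixed effect, using the same two categories as the minimisation and the primary model: fewer than two, or two or more, moderate/severe AECOPD in the year before. The model then carries all four allocation factors alongside pre-Dose 1 concentration.

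The cost is one model term and one degree of freedom. No new data are needed: under section 6.9.3 the count is recorded in the eCRF at Visit 1 and entered in the randomisation system.

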11.9.3. Cell-mediated immune response

Cell-mediated immune response as part of secondary endpoints

CMI induced by the NTHi-Mcat candidate vaccine will be evaluated, presenting the frequencies of antigen-specific CD4⁺ T cells per 10⁶ cells. The specific CD4⁺ T cells being identified as the CD4⁺ T cells expressing at least 2 different cytokines/activation markers among CD40L, IL-2, TNF- α , IFN- γ , IL-13 and IL-17 upon *in vitro* stimulation. Descriptive statistics (Min, Q1, Median, Q3 & Max) will be reported for each group at Day 1, Day 91, Day 271 and Day 451. **(Amended 27 March 2019)**

Cell-mediated immune response as part of tertiary endpoints

CMI response as the frequencies of specific CD4⁺ T cells per 10⁶ cells expressing any combination of cytokines/activation markers will be determined. In addition, the T helper profile of the specific T cell response in T helper 1, T helper 2 and T helper 17 based on the specific expression of respectively IFN- γ , IL-13 and IL-17 will be characterized. Descriptive statistics (Min, Q1, Median, Q3 & Max) will be reported for each group at Day 1, Day 91, Day 271 and Day 451. **(Amended 27 March 2019)**

11.9.4. Analysis of selected biomarkers

Descriptive statistics (median, mean, range, standard deviation, first and third quartiles) will be tabulated for each selected biomarker at study start (Day 1) and end of the study (Day 451) and for each AECOPD from first vaccination to study conclusion.

11.9.5. Correlate of protection

An exploratory analysis will be implemented in an attempt to correlate immune responses to vaccination. A specific analysis plan will describe the methodologies to be used for that purpose.

11.10. Analysis of safety

The analysis will be performed on the TVC.

The percentage of subjects with at least one **local AE** (solicited and unsolicited), with at least one **general AE** (solicited and unsolicited) and with any AE during the 7-day (Day 1 – Day 7) or the 30-day (Day 1 – Day 30) follow-up period will be tabulated after each vaccination and overall with exact 95% confidence interval (CI). The same computations will be done for Grade 3 AEs, for related AEs and for Grade 3 related AEs.

The percentage of subjects/doses reporting each individual solicited local (any grade, Grade 3) and general (any grade, Grade 3, related, Grade 3 related) AE during the 7-day (Day 1 to Day 7) follow-up period will be tabulated for each group as follows:

- Overall, the percentage of subjects with the symptom and its exact 95% CI.
- Overall, the percentage of doses with the symptom and its exact 95% CI.

- Per study vaccine dose, the percentage of subjects with the symptom and its exact 95% CI.

The exact 95% CIs will be calculated assuming independence between doses. For fever, additional analyses will be performed by 0.5°C increments.

The verbatim reports of **unsolicited** symptoms will be reviewed by a physician and the signs and symptoms will be coded according to the MedDRA Dictionary for Adverse Reaction Terminology. Every verbatim term will be matched with the appropriate preferred term (PT). The percentage of subjects with unsolicited symptoms during the 30-day follow-up period after any study vaccine dose with its exact 95% CI will be tabulated by group and by MedDRA PT. Similar tabulation will be done for the percentage of doses, for Grade 3 unsolicited symptoms, for unsolicited symptoms that resulted in a medically attended visit, for Grade 3 and causally related unsolicited symptoms and for unsolicited symptoms causally related to vaccination.

The number of subjects who experienced any **pIMD** or any **SAE** from first vaccination up to 12 months post-Dose 2 will be reported.

The number of subjects who experienced any **AE leading to study withdrawal**, from first vaccination up to study conclusion, or any **SAE related to study participation of concurrent GSK medication/ vaccination**, during the entire study period, will be reported.

Pregnancy from first vaccination up to study end for each female subject and pregnancy outcomes will be described in detail.

The percentage of subjects/ dose using **concomitant medication/ product** (any medication/ product, any antipyretic and any antipyretic taken prophylactically, respectively) during the 7-day follow-up period (Day 1 – Day 7) and during the 30-day follow-up period (Day 1 – Day 30) will be summarised per group for each dose and overall per dose.

- **iSRC safety evaluations**

For safety, 4 interim analysis evaluations are planned. iSRC reviews will be done once 60 and 300 subjects complete one month after first vaccination and once 60 and 300 subjects complete one month after second vaccination (see [Figure 3](#)).

Unblinded review of safety data will be done during iSRC evaluations. No individual clinical study report will be written as a result of these safety evaluations.

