3. STUDY DESIGN OVERVIEW

Figure 2 Study design overview

S = Screening Visit; **V** = Visit; **PC** = Phone contact; **D** = Day; **FU** = Follow-up; **BS (1)** = blood sample for humoral immunogenicity; **BS (2)** = blood sample for cell-mediated immunogenicity (CMI), this blood sample will only be collected from a sub-cohort of subjects; **BS (3)** blood sample for biomarkers; **SP** = sputum sample

The allowed maximum interval between Screening Visit and Visit 1 is 29 days. If a delay occurs for an eligible subject so that the interval exceeds 29 days, some study procedures performed during the Screening Visit need to be repeated within 7 days (see [Table 6](#) for more details).

* An AECOPD visit should be scheduled as soon as possible after the onset of AECOPD symptoms (max 96 hours after and, if applicable, preferably before starting treatment with antibiotics). During this visit blood and sputum samples will be collected. In addition, follow-up phone call(s) and/or visit(s) will take place to determine the end of the AECOPD. These contacts will take place at least every 2 weeks until the AECOPD is resolved.

Protocol waivers or exemptions are not allowed unless necessary for the management of immediate safety concerns. Therefore, adherence to the study design requirements, including those specified in the outline of study procedures (Section [6.5](#)), are essential and required for study conduct.

Investigational vaccine and placebo will be administered in addition to standard of care.

- Experimental design: Phase IIB, randomised, observer-blind, placebo-controlled, multi-centric study with two parallel groups.
- Duration of the study: for each subject enrolled, the study will last approximately 15 months from Visit 1 up to study completion (Visit 8).
 - Epoch 001: Screening Visit.
 - Epoch 002: Primary starting at Visit 1 (Day 1) and ending at Visit 8 (Day 451).
- Primary completion Date (PCD): Last Subject Last Visit (LSLV) at Visit 8 (Day 451) or last visit/contact of Epoch 002.

Refer to [glossary of terms](#) for the definition of PCD.

- End of Study (EoS): Last testing results released of samples collected up to Visit 8 (Day 451).

Refer to [glossary of terms](#) for the definition of EoS.

- Study groups:
 - **10-10-3-AS:** Approximately 300 subjects receiving two doses of the AS01_E-adjuvanted GSK Biologicals' NTHi-Mcat investigational vaccine containing 10 µg of PD, 10 µg of PE-PilA, and 3.3 µg of UspA2.

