 - **CONTROL:** Approximately 300 subjects receiving two doses of placebo (PBS).

Table 2 Study groups and epochs foreseen in the study

Study groups	Number of subjects	Age (Min/Max)	Epochs	
			Epoch 001	Epoch 002
10-10-3-AS	~300	40 – 80 years	x	x
CONTROL	~300	40 – 80 years	x	x

Table 3 Study groups and treatment foreseen in the study

Treatment name	Vaccine name	Study Groups	
		10-10-3-AS	CONTROL
10-10-3/AS01E	NTHi-Mcat 10-10-3	x	
	AS01E		
Placebo	Formulation buffer S9b		x

- Control: placebo control (PBS).
- Vaccination schedule: at Visit 1 (Day 1) and Visit 3 (Day 61).
- Treatment allocation: subjects will be minimised by:
 - Age (40 - 59 years or 60 - 80 years).
 - Number of moderate/ severe AECOPD in the previous year (< 2 or ≥ 2).
 - GOLD grade (GOLD 2, GOLD 3 or GOLD 4).
 - Country

All factors will have equal weight in the minimisation algorithm.

Subjects will be randomised using a centralised randomisation system on internet (SBIR) at first dose. Treatment number allocation (without randomisation) will also occur at Dose 2 using SBIR.

- Blinding: observer-blind.

Table 4 Blinding of study epochs

Study Epochs	Study Groups	Blinding
Epoch 001	10-10-3-AS / CONTROL	observer-blind
Epoch 002	10-10-3-AS/ CONTROL	observer-blind

- Sampling schedule:
 - **Blood samples for assessment of humoral immunogenicity** will be collected from all subjects at Visit 1 (Day 1), Visit 2 (Day 31), Visit 3 (Day 61), Visit 4 (Day 91), Visit 6 (Day 271), Visit 8 (Day 451) and at each AECOPD visit from first vaccination to study conclusion.
 - **Blood samples for assessment of cell-mediated immunogenicity (CMI)** will be collected from all subjects in the CMI sub-cohort at Visit 1 (Day 1), Visit 4 (Day 91), Visit 6 (Day 271) and at Visit 8 (Day 451).
 - **Blood samples for biomarkers** will be collected from all subjects at Visit 1 (Day 1), Visit 8 (Day 451) and at each AECOPD visit from first vaccination to study conclusion.
 - **Sputum samples** will be collected from all subjects at Visit 1 (Day 1), Visit 4 (Day 91), Visit 5 (Day 181), Visit 6 (Day 271), Visit 7 (Day 361), Visit 8 (Day 451) and at each AECOPD visit from first vaccination to study conclusion.
- **COPD symptoms:** All subjects will be asked to record COPD symptoms in their electronic Diary Card:
 - Daily in the morning throughout the study (including during AECOPD): **morning symptoms questionnaire**.
 - Daily in the evening throughout the study (including during AECOPD): **EXACT-PRO questionnaire**.

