9.2.2. Pregnancy

Female subjects who are pregnant or lactating at the time of vaccination must not receive additional doses of study vaccines but may continue other study procedures.

While pregnancy itself is not considered an AE or SAE, any adverse pregnancy outcome or complication or elective termination of a pregnancy for medical reasons will be recorded and reported as an AE or a SAE.

Note: The pregnancy itself should always be recorded on an electronic pregnancy report.

The following should always be considered as SAE and will be reported as described in Sections 9.4.1 and 9.4.3:

- Spontaneous pregnancy loss, including:
 - spontaneous abortion, (spontaneous pregnancy loss before/at 22 weeks of gestation)
 - ectopic and molar pregnancy
 - stillbirth (intrauterine death of foetus after 22 weeks of gestation).
- Any early neonatal death (i.e. death of a live born infant occurring within the first 7 days of life).
- Any congenital anomaly or birth defect (as per [CDC MACDP] guidelines) identified in the offspring of a study subject (either during pregnancy, at birth or later) regardless of whether the foetus is delivered dead or alive. This includes anomalies identified by prenatal ultrasound, amniocentesis or examination of the products of conception after elective or spontaneous abortion.

Furthermore, any SAE occurring as a result of a post-study pregnancy AND considered by the investigator to be reasonably related to the study vaccines will be reported to GSK Biologicals as described in Section 9.4.3. While the investigator is not obligated to actively seek this information from former study participants, he/she may learn of a pregnancy through spontaneous reporting.

9.3. Detecting and recording adverse events, serious adverse events and pregnancies**9.3.1. Time period for detecting and recording adverse events, serious adverse events and pregnancies**

All AEs starting within 29 days following administration of each dose of study vaccines (Day 1 to Day 30) must be recorded into the appropriate section of the eCRF, irrespective of intensity or whether or not they are considered vaccination-related.

The time period for collecting and recording SAEs will begin at the first receipt of study vaccines and will end at last study visit for each subject. See Section [9.4](#) for instructions on reporting of SAEs.

All AEs/SAEs leading to withdrawal from the study will be collected and recorded from the time of the first receipt of study vaccines.

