In addition to the above-mentioned reporting requirements and in order to fulfil international reporting obligations, SAEs that are related to study participation (i.e. protocol-mandated procedures, invasive tests, a change from existing therapy) or are related to a concurrent GSK medication/vaccine will be collected and recorded from the time the subject consents to participate in the study until she/he is discharged from the study.

The time period for collecting and recording pregnancies will begin at the first receipt of study vaccines and will end at last study visit. See section [9.4](#) for instructions on reporting of pregnancies.

The time period for collecting and recording of pIMDs will begin at the first receipt of study vaccines and will end at last study visit. See section [9.4](#) for instructions on reporting of pIMDs.

An overview of the protocol-required reporting periods for AEs, SAEs, and pregnancies is given in [Table 20](#).

Table 20 Reporting periods for collecting safety information

Event	Screening Visit*	Visit 1 Dose 1	6 d post Dose 1	29 d post Dose 1	Visit 3 Dose 2	6 d post Dose 2	29 d post Dose 2	6 months post Dose 2	Study Conclusion
Timepoint		Day 1	Day 7	Day 30	Day 61	Day 67	Day 90	Day 241	Day 451
Solicited local and general AEs									
Unsolicited AEs									
AEs/SAEs leading to withdrawal from the study									
SAEs									
SAEs related to study participation or concurrent GSK medication/vaccine									
Pregnancies									
pIMDs									
Intercurrent medical conditions									

* i.e. consent obtained.

The double-bordered lines indicate timings of vaccination.

AE = adverse event; SAE = Severe adverse event; GSK = GlaxoSmithKline; pIMD = potential immune mediated diseases.

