11.2. Secondary endpoints

Safety:

- Occurrence of each solicited local AE, during the 7-day follow-up period (Day 1 - Day 7) following each vaccination.
- Occurrence of each solicited general AE, during the 7-day follow-up period (Day 1 - Day 7) following each vaccination.
- Occurrence of any unsolicited AE, during the 30-day follow-up period (Day 1 - Day 30) following each vaccination.
- Occurrence of any pIMD from first vaccination up to study conclusion.
- Occurrence of any SAE from first vaccination up to study conclusion.

Efficacy: All AECOPD

- Yearly rate of all AECOPD (any cause, any severity) starting 1 month post-Dose 2, in vaccinated and control subjects.
 - Rate of moderate and severe AECOPD cases in vaccinated and control subjects, during 3, 6 and 9 months observation starting 1 month post-Dose 2.
 - Rate of all AECOPD cases in vaccinated and control subjects, during 3, 6, 9 and 12 months observation starting 1 month post-Dose 2.
 - Rate of all AECOPD cases in vaccinated and control subjects, during 3, 6, 9 and 12 months observation starting 1 month post-Dose 2, by severity.
- Time to first moderate or severe AECOPD.
- Time to first AECOPD of any severity.
- Time to first AECOPD, by severity.
- Duration of moderate and severe AECOPDs.
- Duration of AECOPDs of any severity.
- Duration of AECOPDs, by severity.

Efficacy: AECOPD associated to bacteriological pathogens (PCR)

- Rate of NTHi-associated and/ or Mcat-associated moderate and severe AECOPD, over a period starting 1 month post-Dose 2 and lasting for 1 year.
- Rate of NTHi-associated and/ or Mcat-associated any severity AECOPD, over a period starting 1 month post-Dose 2 and lasting for 1 year.
- Rate of NTHi-associated and/ or Mcat-associated AECOPD, over a period starting 1 month post-Dose 2 and lasting for 1 year, by severity.
- Time to first moderate or severe NTHi-associated and/ or Mcat-associated AECOPD.
- Time to first NTHi-associated and/or Mcat-associated AECOPD of any severity.
- Time to first NTHi-associated and/or Mcat-associated AECOPD, by severity.
- Duration of moderate and severe NTHi-associated and Mcat-associated AECOPD.
- Duration of NTHi-associated and/or Mcat-associated AECOPDs of any severity.
- Duration of NTHi-associated and/or Mcat-associated AECOPD, by severity.

Immunogenicity and CMI:

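### Section 11.10 closes the main SAE and pIMD count at 12 months after Dose 2, about a month before the study conclusion at which the endpoints and data collection end

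*Protocol*

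**What the plan says.** Three parts of the protocol set a time window for SAEs and pIMDs.

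- **Endpoints.** Section 11.2, repeated in the synopsis, lists as secondary safety endpoints "Occurrence of any SAE from first vaccination up to study conclusion" and "Occurrence of any pIMD from first vaccination up to study conclusion".
- **Collection.** Section 9.3.1 starts SAE recording at the first dose and says that it "will end at last study visit for each subject". For pIMDs it says that "collecting and recording of pIMDs will begin at the first receipt of study vaccines and will end at last study visit".
- **Analysis.** Section 11.10, which works on the total vaccinated cohort (TVC), says that the number of subjects with any pIMD or any SAE "from first vaccination up to 12 months post-Dose 2 will be reported".

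The sentences that follow in Section 11.10 use longer windows. AEs leading to study withdrawal are reported to study conclusion, SAEs related to study participation or to a concurrent GSK product over the whole study period, and pregnancies to study end.

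**The concern.** The endpoints and the collection rules agree, and only the analysis rule stops earlier. The one-year follow-up starts one month after Dose 2, so study conclusion falls about 13 months after Dose 2, not 12. A programmer following Section 11.10 literally would leave collected events out of the table meant to report two secondary endpoints.

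This matters most for pIMDs. The risk table in Section 1.4.1 names vaccine-induced autoimmune disease as the only risk attached to the vaccine itself, and close pIMD monitoring as part of the mitigation. The last planned unblinded safety review (Section 9.10.2) comes when about 300 subjects are one month past Dose 2. Apart from ad hoc reviews, the final analysis is therefore the only planned between-group look at late events.

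There is also a definitional gap. The TVC (Section 11.5.2) includes subjects with a single dose, and Section 7.5 lets subjects who may not receive Dose 2 continue other study procedures. For them, a cut-off counted from Dose 2 has no meaning.

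**Working it through.** **Inputs**

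- Dose 2 is at Visit 3, Day 61, and study conclusion is Visit 8, Day 451 (Section 3).
- Allowed intervals (Table 8): Visit 1 to Visit 3, 60 to 75 days; Visit 3 to Visit 4, 30 to 45 days; Visit 4 to Visit 8, 360 to 390 days.
- Month convention: Table 20 places "6 months post Dose 2" at Day 241.
- Planned enrolment is about 600 with 15% dropout (Section 11.4). The dropout rate is a planning assumption.

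**Reproducing the protocol's own days**

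- Visit 8: 61 + 30 + 360 = Day 451, as stated.
- Table 20: 61 + 6 × 30 = Day 241, as stated, so the protocol counts 30-day months there.

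**Time from Dose 2 to Visit 8**

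- Nominal and minimum: 30 + 360 = 390 days.
- Maximum: 45 + 390 = 435 days.

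**Uncounted time = (Dose 2 to Visit 8) − 12 months**

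| 12 months taken as | Nominal cut-off | Gap, nominal and minimum | Gap, maximum |
|---|---|---|---|
| 365 days | 61 + 365 = Day 426 | 390 − 365 = 25 days | 435 − 365 = 70 days |
| 360 days (30-day months) | 61 + 360 = Day 421 | 390 − 360 = 30 days | 435 − 360 = 75 days |

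**Share of follow-up after Dose 1 (365-day year)**

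- Dose 1 to Visit 8, minimum: 60 + 30 + 360 = 450 days. Share: 25/450 = 5.6%.
- Dose 1 to Visit 8, maximum: 75 + 45 + 390 = 510 days. Share: 70/510 = 13.7%.

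**Person-time (365-day year)**

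- Completers: 0.85 × 600 = 510 subjects.
- Nominal: 510 × 25/365 = 34.9 person-years.
- Upper bound: 510 × 70/365 = 97.8 person-years. This requires every completer to use the full Visit 4 and Visit 8 windows.

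**After the correction.** With the window ending at Visit 8, the uncounted time is 0 days under either month convention, and one-dose subjects have a defined end point.

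**The case against.** The strongest reply is that one sentence is out of step and the rest of the protocol points to full coverage. Section 11.12.1 finalises the endpoint analyses on all data up to and including Visit 8, and Section 10.2.1 uses all data collected up to withdrawal. Section 11.5.2 describes a one-year period from Day 90 that lasts until study conclusion. On this view, the phrase in Section 11.10 is a slip for 12 months after the Day 91 visit.

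A slip is plausible, and nothing shows an intention to discard data. But neither general statement overrides a specific window. Section 11.10 names the full period for other events in its next sentences, so a literal reader has reason to treat the shorter window as deliberate.

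Other parts of the reply limit the consequence, and they stand:

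- A reader might infer that all late events vanish from the analysis. They do not. AEs and SAEs leading to withdrawal, and SAEs related to study participation or a concurrent GSK product, are reported to the end. Section 9.3.1 illustrates the study-participation category by protocol procedures, invasive tests and changes of therapy, so it does not cover late SAEs in general.
- A reader might infer that late hospitalised exacerbations go unanalysed. They are severe AECOPD by definition (Table 1) and are compared by group over the one-year efficacy period and cumulatively to Month 15 (Section 11.8).
- Late SAEs and pIMDs are still collected and reported to the sponsor within 24 hours (Section 9.4), so individual case reporting is unaffected.
- Secondary comparisons are descriptive (Section 11.11), so no test or success criterion depends on the count.

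**Conclusion.** The analysis window in Section 11.10 contradicts the endpoint definitions in Section 11.2 and the collection period in Section 9.3.1, and it is wrong as written. On the nominal schedule it leaves 25 days per completer out of the main SAE and pIMD count, about 6% of post-Dose 1 follow-up. The figure of roughly 35 person-years assumes 510 completers and a 365-day year. The 70-day figure is an upper bound, not a typical value. On 30-day months the range is 30 to 75 days. These figures apply to two-dose subjects who complete within the Table 8 windows.

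The events affected are late SAEs outside the categories that Section 11.10 reports to the end, and late pIMDs that do not lead to withdrawal. A reader might conclude that the two secondary safety endpoints are not delivered at all. That goes too far: on the nominal schedule the count covers 425 of 450 days (94%), and the missing data are collected. The point is a moderate consistency correction. The statistical analysis plan was not available, and it may already use the right window; the protocol text would still need to agree with it.

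**What to change.** In Section 11.10, end the reporting window for both SAEs and pIMDs at study conclusion (the last study visit), in place of 12 months after Dose 2. This matches Sections 11.2 and 9.3.1 and also covers one-dose subjects in the TVC. If a fixed 12-month figure is wanted, keep it as a supplementary table and state how a month is counted and what applies to subjects without Dose 2.

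The cost is one phrase. No data, visits or procedures change. Correcting the protocol before analysis also avoids having to describe and justify a departure from the stated plan in the final report, as Section 11.12 requires.
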